1.1. Rationale and Objective: While there is support in the literature for beneficial effect of XO inhibitor therapy on GFR and BP in pediatric CKD, the degree of expected change in GFR based on disease etiology is uncertain. Therefore, we propose a randomized controlled trial of hyperuricemic pediatric CKD participants in a 2:1 allocation between Allopurinol and standard of care (SOC) therapy, and stratified by disease etiology (cohort A: non-glomerular, cohort B: glomerular). Randomization procedure will be blinded, but the allocation will be unblinded to investigator and participant because of the lack of placebo. Allopurinol will be titrated to reach a normal range of serum UA 3-5 mg/dL by 6 months. Local SOC practice for pediatric CKD includes control of blood pressure with anti-hypertensives, control of acidosis, control of proteinuria, and frequent laboratory monitoring to measure the rate of renal function decline. The primary outcome of Aim 1A is change in GFR between baseline and 6 months by treatment group. The secondary outcomes are change in serum UA, and change in BP over the same time. An exploratory sub-aim (Aim 1B) will identify and compare GFR change by cohort characteristics (disease etiology, proteinuria, and race) that may influence future trial designs.

1.2. Experimental Design (Table 1): We will conduct a 6-month randomized treatment (Allopurinol) vs. SOC clinical trial to measure change in GFR over time in pediatric hyperuricemic CKD participants. We will conduct this study after obtaining appropriate consent and assent. Our recruitment pool will include all patients receiving medical care from the CHoR Pediatric Nephrology Division, new and recurring outpatient encounters. The division currently sees approximately 3,500 outpatient encounters per year. The study visits will coincide with SOC visits with the possible exception of visit V1A (some but not all participants will normally be seen for SOC 1 month after the baseline visit). The following inclusion and exclusion criteria apply:

- Inclusion Criteria: CKD stage 1-5; Age 2-20 years old at time of enrollment; Hyperuricemic
- Exclusion Criteria: Contraindication to Allopurinol; Elevated baseline liver function tests; Receiving acute or chronic dialysis; Primary metabolic disorder; Sickle cell disease; Autosomal Dominant Polycystic Kidney Disease; Cystinosis; Bartter or Gitelman Disease; Pregnant or nursing.

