The allocation will be unblinded to investigators and participants. We plan to over-sample the glomerular cohort B and limit enrollment of the non-glomerular cohort A to ensure adequate distribution of the sample by disease etiology in a proportion generalizable to the national pediatric CKD population (2:1). The proposed allocation distribution is detailed in Section 1.3 and Table 2.

Hyperuricemia is defined in this protocol as having at least two measures of serum UA ≥ 5.5 mg/dL in the last 12 months, or actively treated with a XO inhibitor for a previous diagnosis of hyperuricemia. Participants actively treated with a UA lowering agent (Allopurinol, Febuxostat, or Losartan) will undergo a washout period of a minimum of 1 month (up to 3 months) prior to enrollment in the trial, then randomized to treatment versus control groups. None of the patients in the CHoR Pediatric Nephrology group practice actively treated with these agents had/have symptomatic hyperuricemia, and only 3 out of 14 treated have reached the target UA level of 3-5 mg/dL which will be applied in this study protocol. As it is unknown to what degree patients are benefiting from a minimal reduction of UA but with a persistent hyperuricemia, the CHoR Pediatric Nephrology Division has concluded that it is ethical for consenting participants actively receiving a XO inhibitor to be randomly assigned to treatment or control after a wash-out period.

Allopurinol dose will be initiated using standard weight-based dosing at the Baseline Visit 1 (V1), and titrated at Visits 1A and 2 (V1A, V2) to achieve a goal UA level in the normal range of 3-5 mg/dL by Visit 3 (V3).

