Participants will be recruited during a standard of care (SOC) visit and consented at that visit or by phone if they meet study criteria. Subjects will be randomized in a blinded manner to treatment or control groups at the time of consent if they do not require a washout or medication conversion. If they do require a washout or medication conversion to Candesartan, the randomization will occur once the washout is completed and after a If applicable, the Allopurinol washout and/or Candesartan conversion will be initiated 4 weeks before the participant's next scheduled SOC visit. In the case of Allopurinol washout, the PI or research coordinator will provide the participant with the Allopurinol stop-date and call the participant to remind them to discontinue within 7 days of the medication change. Uric acid level will be measured with SOC labs at their next SOC visit and if participants are hyperuricemic (UA \geq 5.5 mg/dL), will continue in the trial in their pre-determined treatment group. However if participants are normouricemic (UA <5.5 mg/dL), UA will be checked again at their next SOC visit up to 3 months later, and participants will proceed in the trial if they are then hyperuricemic. Otherwise they will be withdrawn from the trial, and their primary nephrology provider will decide whether to resume or discontinue Allopurinol treatment off-study at their own discretion.

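### Randomization timing is stated inconsistently and Aim 1A has no single named primary analysis: fix one order with eligibility results first, and adjust the primary model for cohort and baseline GFR

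*Combined protocol and SAP*

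**What the plan says.** **Timing.** Section 1.2 requires a washout "prior to enrollment in the trial, then randomized to treatment versus control groups". Table 1 puts enrolment and randomization at V1 (month 0). The recruitment section says that for those needing washout or conversion "the randomization will occur once the washout is completed"; the sentence then breaks off in the available text. The same paragraph says that participants are "consented at that visit or by phone if they meet study criteria", that they are randomized "to treatment or control groups at the time of consent if they do not require a washout or medication conversion", and that those still hyperuricemic at the uric acid check after washout "will continue in the trial in their pre-determined treatment group". Study Intervention Administration triggers the Candesartan conversion by the drugs a participant is prescribed when randomized.

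**Eligibility.** Section 1.2 excludes anyone with "Elevated baseline liver function tests" or who is "Pregnant or nursing". In Table 1 the comprehensive panel (item D) first appears at V1, and only the basic panel (item C) comes earlier. The pregnancy test (item G) appears only in the treatment-group row, including in the column before V1.

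**Analysis.** Section 1.3 assigns two-sample t-tests on GFR change to Aim 1A and 2-way ANOVA with interaction to Aim 1B. It also plans repeated-measures ANOVA over all three time points by intention to treat. It states neither the covariates of that last model nor which analysis is primary. Allocation is 2:1, stratified by etiology, and open to investigators and participants.

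**The concern.** Allocation is known to everyone, so any exclusion decided after it can differ by arm. The recruitment section allows withdrawal on the uric acid result and, at the nephrologist's discretion, on blood pressure. If a site read the plan as allocating before these checks, the withdrawals would be post-randomization exclusions, contrary to the intention-to-treat statement in the Data and Safety Monitoring Plan. Likewise, a liver or pregnancy result that arrives after allocation, or a pregnancy test done in one arm only, screens the arms differently. With 14 planned controls, a few such exclusions count.

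The analysis question is separate. The trial stratifies by etiology because etiology is expected to affect GFR decline; Background and Significance says glomerular disease often progresses faster. An unadjusted comparison leaves that factor out. With two analyses of the same outcome and no ranking, the choice between them could be made after the data are seen.

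**Working it through.** **1. The order of events, side by side**

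| Place | Who | What it implies |
|---|---|---|
| Section 1.2 | washout | washout, enrolment, then allocation |
| Table 1 | everyone | allocation at V1 |
| Recruitment, randomization sentence | washout or conversion | allocation after washout |
| Recruitment, same paragraph | no run-in | allocation at consent |
| Recruitment, uric acid check | washout | group already fixed when the result is read |
| Study Intervention Administration | conversion | allocation first, then conversion |
| Table 1, identification column | everyone | different tests by arm before V1 |

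The first three rows agree. The last three cannot be followed as written under that order. The fourth conflicts with Table 1 only when consent and V1 fall on different days. That is clear for phone consent, whose frequency is not given. About 1/4 of participants are expected to convert (42/4 = 10.5), so at most 42 − 10.5 = 31.5 need no run-in. This is a ceiling, not an estimate of those affected.

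**2. The plan's own power**

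Inputs from Section 1.3: difference 3, SD 3.5, one-sided α 0.05, 28 against 14.
- Standard error = 3.5 × √(1/28 + 1/14) = 1.146.
- Noncentrality = 3/1.146 = 2.62 on 40 df.
- Power = 82.4%, which reproduces the stated 80% or more. At 26:13 it is 79.7%, so 42 is the smallest exact 2:1 total that reaches 80%.

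**3. Cohort mix in Table 2**

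- Non-glomerular share: 19/28 = 0.679 on Allopurinol, 7/14 = 0.500 in control; gap 0.179.
- Shift in the unadjusted difference = 0.179 × cohort difference in mean change. For assumed differences of 1, 2 and 3 it is 0.18, 0.36 and 0.54 ml/min/1.73m², or 6%, 12% and 18% of the planned 3. If non-glomerular patients do better, the shift favours Allopurinol.
- By simulation with these cells fixed and an assumed within-cell SD of 3.5, the one-sided type I error is roughly 7%, 8% and 9% instead of 5%.
- Table 2 does not fit the text. Cohort A totals 19 + 7 = 26, but Section 1.3 limits it to 19. The within-cohort ratios are 19/7 = 2.71 and 9/7 = 1.29, not 2.

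**4. Cost of adjusting**

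- Information without adjustment: 28 × 14/42 = 9.33.
- With cohort adjustment and Table 2 cells: 19 × 7/26 + 9 × 7/16 = 5.12 + 3.94 = 9.05.
- Variance ratio = 9.33/9.05 = 1.03.
- With two further df spent (38 df), power is 81.3% if the covariates explain nothing. With partial correlation ρ the SD becomes 3.5√(1 − ρ²), and power is 82.6%, 84.4% and 90.0% for assumed ρ of 0.2, 0.3 and 0.5.

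**5. Does the model recover power from missing visits?**

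Assume a missing rate m at each follow-up visit, independently, and a 3-to-6-month correlation r of 0.5 to 0.8. Information per person is (1−m)² × inverse[[1,r],[r,1]] + m(1−m) × I, and effective n = 42 divided by the month-6 element of its inverse. At m = 5% this gives 40.4 to 41.2, against 39.9 completers. After charging the 3% variance and two df:

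| m | model | completers' t-test |
|---|---|---|
| 5% | 79.9–80.5% | 80.6% |
| 10% | 78.3–79.6% | 78.6% |
| 20% | 74.5–77.2% | 74.1% |

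There is no dependable gain at plausible rates.

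**The case against.** The strongest reply is that the plan already has the right order. Section 1.2, Table 1 and the explicit randomization sentence agree. The section heading itself calls the medication adjustments pre-trial, and the Data and Safety Monitoring Plan tracks retention from washout or conversion to study initiation. Figure 1, a decision tree, is not shown and may settle the matter. Participants consent only if they meet criteria, hyperuricemia is defined from the last 12 months' values, and study visits coincide with routine visits, so consent and V1 can be one visit.

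Most of this stands. A reader might infer that run-in participants are allocated before washout and that their withdrawals are therefore post-randomization exclusions. The documents do not support that: under the better supported order there are none. What remains is that conflicting sentences stay in force whatever Figure 1 shows, and that the plan does not say which liver and pregnancy results establish eligibility at consent.

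On analysis, a t-test on change is valid if allocation is truly 2:1 within each cohort. A repeated-measures analysis is already planned, and etiology enters the Aim 1B models. So it would be wrong to say that the plan has no longitudinal analysis or never uses cohort. It would also be wrong to state as fact that incomplete cases are dropped, since no missing-data rule is given. The missing-data power argument fails (step 5). Table 2 may be a misprint, in which case the size of the shift falls away. The case for adjusting for a stratification factor does not.

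**Conclusion.** Two points hold, and both should be corrected.

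First, the timing of randomization is inconsistent in the legible text, and the scheduled eligibility tests are not tied to it. The conflict is clear for phone consent, for the group said to be already fixed at the uric acid check, for the conversion trigger, and for the one-armed pregnancy test. How many participants this affects cannot be computed from the documents.

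Second, Aim 1A lacks one named primary analysis, and the t-test as described omits the stratification factor. The shift of 0.18 to 0.54 ml/min/1.73m² rests on Table 2 as printed and on assumed cohort differences of 1 to 3.

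A reader might also infer that the sample size is wrong. It is not: 42 gives 82.4% power under the stated assumptions.

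**What to change.** **Order.** State once that nobody is randomized until any washout or conversion is complete and the protocol's existing eligibility results are in hand. Delete the wording about a pre-determined group, and reconcile randomization at consent with Table 1's V1. Make Table 1's data collection before randomization identical for both arms. Count run-in failures as not randomized, and analyse everyone randomized. Study Intervention Administration and the recruitment section must be reconciled on when conversion is triggered; no clinical rule is proposed here.

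**Analysis.** Name one primary analysis for Aim 1A: the repeated-measures model already planned, fitted by likelihood to the 3- and 6-month GFR. Include treatment, visit, treatment-by-visit, baseline GFR and cohort, with the 6-month treatment contrast primary. Report missing 6-month GFR by arm. Reconcile Table 2 with the cohort A limit of 19 and with 2:1 allocation within cohort.

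**Cost.** Mostly wording. Allocation may wait briefly for results, pregnancy tests would also be done in participants later allocated to control, and more people may need to be consented because run-in failures do not count toward 42. The model costs about 3% in variance and two df (82.4% to 81.3% if the covariates explain nothing) and relies on data missing at random given the observed GFRs.

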2.2. Experimental Design: The study design of Aim 2 is the same as Aim 1 (see **Table 2**). We will measure the following biomarkers from reserved serum and urine samples at the baseline, 3, and 6 month visits. Activity of the Nlrp3 inflammasome will be measured via: serum high sensitivity CRP, Xanthine Oxidase

activity level, Nlrp3, Interleukins 1 β and 18, and urine Nlrp3 and IL-18. Renal injury biomarkers will be measured from serum NGAL, urine NGAL, NAG, KIM-1, and ET-1.

2.3. Statistical Analysis: We will report means/medians and standard deviations (SD)/interquartile range (IQR) for all continuous measures. Similar analyses will be used for Specific Aim 2 as Specific Aim 1. All sample size calculations were performed with nQuery Advisor v.7.0.

STUDY INTERVENTION ADMINISTRATION

The proposed intervention uses a study drug (Allopurinol) and concomitant therapy (Candesartan) that are available as generic. The PI is proposing to study the effects of Allopurinol under FDA-approved indications, which is approved for use in children and adults for the reduction of high uric acid levels. Candesartan is approved for use in children and adults for the reduction of high blood pressure. The concomitant therapy, Candesartan, is required in this protocol to reduce drug-drug interactions with Allopurinol. The medications Lisinopril, Enalapril, and Benazepril are commonly prescribed for hypertension but increase the risk of moderate to severe adverse reactions when used concomitantly with Allopurinol. Losartan is also a blood pressure lowering medication that uniquely lowers uric acid levels which could affect the results of the trial, but does not interact with Allopurinol so will be converted for a different and specific reason. Any participant in the trial who is prescribed Lisinopril, Enalapril, Benazepril, or Losartan at the time of randomization will be converted to a similar or same class of blood pressure lowering medication, Candesartan, which does not interact with Allopurinol or lower uric acid levels. Approximately 1/4 of participants in this trial will qualify for the Candesartan conversion. Candesartan will be supplied by the investigational pharmacy at no cost to participants. Allopurinol will also be supplied by the investigational pharmacy to the treatment group participants.

[figure not shown]
Recruitment and pre-trial medication adjustments:

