In the case of Candesartan conversion, the PI along with consultation from the participant's primary nephrologist will prescribe the starting dose of Candesartan. The PI or research coordinator will instruct the participant to STOP Losartan/Lisinopril/Benazepril/Enalapril and START Candesartan on a specific date scheduled 4 weeks before their next SOC visit. The research coordinator or PI will confirm the start/stop date with the participant by phone within 7 days, and if unable to reach the participant or his/her guardian, the Candesartan will NOT be mailed to the participant by the investigational pharmacy. The participant's BP will be checked at their next SOC visit as part of routine care, and their primary nephrologist will make adjustments to the medication as necessary to achieve adequate BP control. If a participant decreases or remains in the same stage of hypertension (as defined by national pediatric BP guidelines) as before the Candesartan conversion (for example, remains in Stage 1 hypertension pre- and post-Candesartan, or moves from Stage 1 to normal pre- and post-), then the participant may continue in the trial. If, however, the participant increases in hypertension stage pre- and post-Candesartan conversion (for example, normal to Stage 1 hypertension pre- and post-) the primary nephrologist will either adjust the Candesartan dose or decide to withdraw the participant from the trial and revert back to the prior medication as they deem necessary. Similarly, if the BP is determined to be too low, the dose will be adjusted or discontinued by the primary nephrologist. Signs and symptoms of low BP will be reviewed with participants prior to the conversion, and participants will be

encouraged to report any symptoms once they are converted. Participants who experience side effects, or those that are withdrawn from the study due to Candesartan conversion will be reported to the PI/research coordinator and Independent Monitor. The Data and Safety Monitoring Plan documents will review this in more detail.

Figure 1. Washout and Medication Conversion Decision Tree

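### If the Candesartan confirmation call fails, the readable text withholds the new drug but does not withdraw the dated instruction to stop the old one

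*Combined protocol and SAP*

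**What the plan says.** The conversion procedure is in the Study Intervention Administration section, under the pre-trial medication adjustments. Its steps, in the order of the text, are:

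1. The investigator or coordinator is to "instruct the participant to STOP Losartan/Lisinopril/Benazepril/Enalapril and START Candesartan on a specific date scheduled 4 weeks before their next SOC visit".
2. One of them "will confirm the start/stop date with the participant by phone within 7 days".
3. The same sentence adds that, if neither participant nor guardian can be reached, "the Candesartan will NOT be mailed to the participant by the investigational pharmacy".
4. After that, "The participant's BP will be checked at their next SOC visit as part of routine care".
5. If the hypertension stage has risen at that check, the primary nephrologist either adjusts the Candesartan dose or may "decide to withdraw the participant from the trial and revert back to the prior medication as they deem necessary".

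The opening of the same section makes the investigational pharmacy the source of Candesartan and gives the size of the group: "Approximately 1/4 of participants in this trial will qualify for the Candesartan conversion". The procedure refers to the monitoring plan for more detail, and Figure 1 is a decision tree for washout and conversion.

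**The concern.** The instruction has two halves, stop and start, tied to one date. The rule for a failed call acts on only one of them: the new drug is not sent. Nothing in the readable text tells the family that the stop half has lapsed, makes stopping depend on having Candesartan in hand, or gives another way of reaching them. Staff cannot be assumed to put this right later, because the rule applies precisely when the family has not been reached.

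What is at stake is the safety of children with CKD. The Background names hypertension among the factors that speed progression, and Section 1.1 lists blood pressure control as part of local standard care. A family that follows the stop half alone would have no blood pressure drug from this procedure until the next scheduled check.

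**Working it through.** No stated figure is in dispute, so the check is mainly a reading of the text, followed by simple arithmetic for size.

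**Does the timing of the call remove the gap?** The 7 days have no stated anchor. The parallel sentence on Allopurinol washout ties its 7 days to the medication change, but does not say clearly whether the call falls before or after it.

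- *Call before the set date.* The call fails and nothing is mailed. The family still holds a stop date that has not been withdrawn.
- *Call after the set date.* The old drug may already have been stopped when the call fails. This reading fits poorly with the paired instruction: if mailing waits for the call, no family could start on the date.
- *Call within 7 days of the instruction being given.* This probably falls before the set date, with the same result as the first case.

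The first reading is the more natural, but the gap remains under all three.

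**Does another readable provision close it?**

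- The return to the prior drug in step 5 is triggered by a rise in hypertension stage at the next visit, not by a failed call.
- Counselling before conversion covers symptoms of low blood pressure. None is described for raised blood pressure.
- The Data and Safety Monitoring Plan adds six-monthly reporting of retention among participants in washout or conversion. It does not mention a failed call.
- Figure 1 could contain such a branch. Its content was not available to us.

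**Length of the possible gap.** From the set date to the next stated blood pressure check: 4 weeks × 7 = 28 days as scheduled.

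**Number exposed.** Inputs: planned sample size 42 (Section 1.3 and Table 2) and a share of about 1/4 needing conversion (Study Intervention Administration).

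- Converters: 0.25 × 42 = 10.5, so about 10 to 11.
- Expected failed calls = 10.5 × f, where f is the failed-call rate. The documents give no value, so f is an assumption:

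| Assumed f | Expected failed calls |
|---|---|
| 5% | 10.5 × 0.05 = 0.525, about 0.5 |
| 10% | 10.5 × 0.10 = 1.05, about 1.1 |
| 20% | 10.5 × 0.20 = 2.1 |

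These count failed calls, not gaps in treatment. The number with a gap is this figure multiplied by the share of unreached families who stop without a replacement. That share is also unknown and is at most 1.

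**The case against.** The strongest reply is that withholding the drug is itself the safeguard. Stop and start are one paired instruction for one date, Candesartan is mailed, and mailing waits for the call. On that reading, no call means no conversion, and a family that receives nothing simply carries on as before. As an account of what was intended, this stands. As an account of what the text says, it does not: the readable prose leaves the family to infer it.

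Figure 1 is also a fair objection. A decision tree is the natural place for a failed-call branch, so the absence can be asserted only for the readable prose.

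Three stronger readings are tempting, and the documents do not support them.

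- *That the protocol contains two contradictory rules.* It is closer to an incomplete rule: one half of the instruction is governed after a failed call and the other is not.
- *That every unreached family goes about 4 weeks untreated.* Only a family that stops although no replacement has arrived would have a gap.
- *That baseline blood pressure or GFR is biased, so that later change reflects re-treatment rather than Allopurinol.* The sentence placing randomization after washout or conversion is incomplete in the text we have, so it is not clear that this visit is the baseline. Nor is it clear that an unconverted participant would proceed. Conversion applies to both arms, so re-treatment in one or two participants would mainly add noise to the randomized comparison.

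**Conclusion.** The point holds as a patient-safety gap in the readable conversion procedure. After a failed call, the text withholds Candesartan and leaves the dated stop instruction neither cancelled nor made conditional. An unreached family that acts on the instruction could be without either drug for about 4 weeks.

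The gap would affect few participants: at most about 2 of the 10 to 11 converters at the top of the assumed range, and possibly none. This rests on a failed-call rate of 5% to 20%, which is our assumption, on mailing being the only route of supply, and on Figure 1 not already covering the case. No effect on the trial's estimates is claimed. The case for acting is that the protocol's own fallback can foreseeably create the gap and that correcting the text is cheap.

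**What to change.** Check Figure 1 first. If it has a failed-call branch, bring the prose into line with it. Otherwise:

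- reconcile the stop/start instruction with the no-mail rule, in both the prose and Figure 1;
- give the 7 days an anchor and state whether the call comes before or after the set date;
- state, in the instruction handed to the family at the outset, what applies if the call is not completed, since an unreached family cannot be told later.

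What that instruction should say clinically is for the sponsor and the treating nephrologists; no rule is proposed here. The cost is about a sentence in the conversion procedure, a matching line in the coordinator's script and, if needed, a branch in Figure 1. Sample size and analysis are unaffected.
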